4.3 Selection of trial population

4.3.1 Consent and recruitment strategy

All adult patients fulfilling the inclusion criteria will be offered enrollment in the study. However, patients who enter the ICU after cardiac surgery are mostly sedated and mechanically ventilated. Biomarker elevations detect a potential renal damage at an early timepoint and interventions have to begin in this early phase to prevent the development of AKI. Therefore, the intervention cannot be delayed until patients regain consciousness. For this emergency situation, the informed consent process hasto follow the legal country-specific regulations. In Germany the informed consent process is defined on the basis ofthe German Civil Code (§ 1902 and § 1904) and on the basis ofthe German Drug Law (§40 and § 41)

The method of obtaining and documenting the informed consent and contents of the consent will complywithICH-GCP and all applicable regulatory requirement(s).

It is strongly recommended to consult a relative or an associated person as soon as possible and to enquire about the patient's presumed wishes and any previous objections towards participation in clinical studies. The information has to be documented in the patient's medical record. Once the patient regains capacity togive informed consent he/ she needs to be asked for his/her informed consent to continue to participate in the study. The relevant forms to this effect are filed in the study folder.

The patient needs to be informed that all data are kept confidential and stored in pseudoanonymized form. He/ she has the right to withdraw study participation at any timewithout giving a reason. A duplicate of the written informed consent needs tobe handed to the patient.

No patient will be excluded from the study on the basis of gender, race, ethnicity or sexual preference. Patients will be identified for recruitment by screening all patients receiving care in the critical care units.

4.3.2 Inclusion criteria

- 1. Patients undergoing cardiac surgery with CPB
- 2. Urinary [TIMP-2]*[IGFBP7] ≥ 0.3 4 h after CPB
- 3. Age between 18 and 90 years
- 4. Written informed consent

4.3.3 Exclusion criteria

None of the following conditions can be fulfilled:

CONFIDENTIAL

Date: 16.02.2017 Version: V1

- 1. Preexisting AKI
- 2. Patients with cardiac assist devices (ECMO, LVAD, RVAD, IABP)
- 3. Pregnancy
- 4. Known (Glomerulo-) Nephritis, interstitial nephritis or vasculitis
- 5. CKD with eGFR< 30 ml/min
- 6. Dialysis dependent CKD
- 7. Prior kidney transplant within the last 12 months
- 8. Participation in another clinical interventional trial in the last 3 months
- 9. Persons with any kind of dependency on the investigator or employed by the institution responsible or investigator
- 10. Persons held in an institution by legal or official order

4.4 Withdrawal of trial subjects after trial start

Once a patient has been enrolled in the study the investigator will make every reasonable effort to keep the patient in the study. However, if the investigator has to withdraw a patient from the study or if the patient refuses further study participation, a final examination should be performed. For patients withdrawn from the study, the follow-up information should be obtained, if possible.

A patient may request to be withdrawn from the study at any time, for any reason, without prejudice. A patient may also be withdrawn from the study at the request of his/her legal representative or physician, for any reason.

4.4.1 Procedures for premature withdrawal from treatment during the trial

The active study participation stops with the end of the intervention period (12h after randomization). Patients who withdraw from active study participation earlier will be requested to permit continued data collection for the remainder of the follow-up period.

4.5 Closure of trial site/ premature termination of the clinical trial

4.5.1 Closure of trial site

The sponsor has the right to terminate the study at a specific study site. Reasons which may require termination are:

Patient enrolment is too slow

CONFIDENTIAL Version: V1

Date:

16.02.2017

- The investigator fails to comply with the study protocol or legal requirements
- Data recording is not accurate, e.g. CRFs are not completed or data entry is not legible.

4.5.2 Premature termination of the clinical trial

The PCI has the right to terminate the trial prematurely if there are any relevant medical or ethical concerns, or if completion of the trial is no longer practical. If such action is taken, the reasons for terminating the trial must be documented in detail. All trial subjects still under treatment at the time of termination must undergo a final examination which must be documented. The PCI must be informed without delay if any investigator has ethical concerns about continuation of the trial.

Premature termination of the trial will be considered if:

- The risk-benefit balance for the trial subject changes markedly
- It is no longer ethical to continue treatment
- The PCI considers that the trial must be discontinued for safety reasons
- Results of other research show that one of the components of the intervention is superior or inferior to another
- It is no longer practical to complete the trial

The PCI decides on whether to discontinue the trial in consultation with Advisory Board and/or statistician.

4.6 Treatment

All patients will receive standard of care therapy. In the validation group, functional hemodynamic monitoring (according to the standard of each center), optimization of fluid status and hemodynamic parameters according to a specific algorithm (see Figure 1), avoidance of hyperglycemia, discontinuation of nephrotoxic drugs if possible, consideration of alternatives to radio contrast agents, discontinuation of ACEiand ARBs, and close monitoring of serum creatinine and urine output will be performed. Further concomitant medication will not be restricted.

4.6.1 Experimental intervention

Four hours after terminating CPB in the context of a cardiac surgery procedure, urinary [TIMP-2]*[IGFBP7] will be measured to identify patients at high risk for AKI. Patients with a value ≥ 0.3 will be randomized as follows to one of the two treatment arms.

CONFIDENTIAL

[figure not shown]
Date: 16.02.2017 Version: V1

The KDIGO guidelines for prevention of acute kidney injury will be strictly implemented:

- Discontinuation of all nephrotoxic agents if possible
- Discontinuation of ACE inhibitors and ARBs forthe first 48 hours after surgery
- Close monitoring of serum creatinine and urinary output
- Avoidance of hyperglycemia by close monitoring for the first 72 hours after surgery
- Consideration of alternatives to radio contrast agents
- Functional hemodynamic monitoring (according to the standard of each center, e.g. PICCO, PAC, TOE)
- Hemodynamic monitoring and optimization according to a hemodynamic algorithm (see Fig. 1)

Figure 1. Hemodynamic algorithm (validation arm)

CI, cardiac index; CO, cardiac output; MAP, mean arterial pressure; PLRT, passive leg raising test

4.6.2 Control intervention

Patients in the control group will receive standard of care. In these patients, cardiac output will also be measured (e.g. via echocardiography; at initiation and then every 3h up to 12h) but the treating physician will not be informed about the values.

(07-Anlt-16) 16.02.2017 Version: V1

Date:

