Patients at high risk of AKI will be identified by measuring NC [TIMP-2]*[IGFBP7] (NephroCheck® Test) 4h after CPB. Patients with NC ≥ 0.3 will be randomized.

Validation group:

Implementation of the KDIGO guidelines:

Optimizing volume status and hemodynamic parameters (according to a hemodynamic algorithm, see **Figure 1.Hemodynamic** algorithm (validation arm), page 23), functional hemodynamic monitoring, discontinuation of all nephrotoxic agents when possible, discontinuation of angiotensin converting enzyme inhibitors(ACEi) and angiotensin receptor blockers (ARB) in the perioperative period to avoid severe hypotension, consideration of alternatives to radiocontrast agents, close monitoring of serum creatinine and urinary output, avoidance of hyperglycemia.

Control group:

The patients will receive standard of care. In these patients, cardiac output will be measured (e.g. by echocardiography, at initiation and then every 3h up to 12h) but the treating physician will not be informed about the values.

Key inclusion and exclusion criteria

Inclusion criteria:

- 1. Adult patients undergoing cardiac surgery with CPB
- 2. [TIMP-2]*[IGFBP7] ≥ 0.3 4h after CPB
- 3. Age between 18-90 years
- 4. Written informed consent

Exclusion criteria:

- Preexisting AKI
- 2. Patients with cardiac assist devices (ECMO, LVAD, RVAD, IABP)
- 3. Pregnancy
- 4. Known (Glomerulo-) Nephritis, interstitial nephritis or vasculitis
- 5. CKD with eGFR< 30 ml/min
- 6. Dialysis dependent CKD
- 7. Prior kidney transplant within the last 12 months
- 8. Participation in another intervention trial in the past 3 months
- Persons with any kind of dependency on the investigator or employed by the institution responsible or investigator
- 10. Persons held in an institution by legal or official order

Primary trial objective

To investigate the adherence to the trial protocol in a multi-center

CONFIDENTIAL

Date: 16.02.2017 Version: V1

	multinational setting as a pilot project for a large randomized controlled					
	trial (feasibility trial). Primary outcome: KDIGO recommendations fulfilled					
	at all time					
Study endpoints	Primary endpoint:					
	Compliance rate (proportion of patients who are treated according to the trial protocol): KDIGO recommendations fulfilled at all time					
	Secondary endpoints:					
	Occurrence of AKI according to the KDIGO guidelines within 72 hours after cardiac surgery					
	Moderate and severe AKI (according to the KDIGO guidelines)					

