4.2.1 Randomization

Prior to being randomized into the study, patients will have:

- Signed a written informed consent
- Completed screening
- Met all designated inclusion criteria and have no exclusion criteria

Randomization assignment (in a 1:1 ratio to the two treatment arms) will be given only to those patients fulfillingthe inclusion and none of the exclusion criteria and providing informed consent. Randomization will be performed by using a web-based randomization system. After identifying a high risk patient (urinary [TIMP2]*[IGFBP7] ≥ 0.3, NephroCheck® Test), patients will be assigned to control or intervention group, whereas the intervention will be provided by research staff not involved in the care of patient.

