4.2.2 Blinding

Study intervention will be performed by research staffnot involved in anesthesia, perioperative care, and endpoint assessment.In the control group, the independent research staff will carry out the hemodynamic evaluation so that the trial is still blinded. General anesthesia and perioperativecarewill be performed in all patients by an experienced anesthesia team. Thus, blinding concerns i) the individual patient, ii) investigators obtainingdata, follow-up visits and documentation, and iii) the endpoint committee. Group allocation will not be unfolded until final statistical analysis.

Intention-to-treat analysis will address attrition bias. To prevent publication bias in future metaanalyses, results are intended to be published irrespective of the outcome of the trial.

CONFIDENTIAL

Date: 16.02.2017 Version: V1

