4.6.3 Additional treatments

The patient's primary physicians will determine the remainder of patient management consistent with established best practices with the management of critically ill patients. In patients with acute lung injury (ALI) or acute respiratory distress syndrome (ARDS), tidal volume for mechanical ventilation will be approximately 6 ml per kilogram of predicted body weight and adjusted to maintain a peak plateau pressure between 25 and 30 cm of water(24). Ventilator associated pneumonia will be evaluated and treated in accordance with published clinical practice guidelines and consensus statements(25). Sepsis will be diagnosed and treated in accordance with published guidelines(26). All medications will be dose adjusted for renal failure and RRT in accordance with standard dosing guidelines.

All patients will be prescribed a nutritional intake that will provide at least 25-30 kcal/kg/day, depending on mechanical ventilation and other factors. Protein intake will be at least 1.2 g/kg/day. In patients receiving parenteral nutrition, carbohydrate infusion rates will not exceed 5 mg/kg/min. Water-soluble vitamins will be supplemented to replace dialysis-related losses.

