4.7.1.3 Visits in detail

	T1 Base- line	T2 ¹ OD, interve ntion time	T3 POD 1	T4 POD 2	T5 POD 3	T6 Dis- charge	T7 Follow- up ²
Inclusion and exclusion criteria	X						
Randomization	Х						
Demographic Data (age, gender, BMI)	Х						
Medical history(preexisting condition, premedication)	Х						
Operation data (type of surgery, CPB time, X-clamp time, transfusion)	X						
Respiratory parameter	Χ	Χ					
Hemodynamic parameters (MAP, HR, CVP, CI, CO)		X					
Laboratory parameter (lactate, hemoglobin, electrolytes)	X	X	Х	X	Х		
Renal parameter (BUN, creatinine, GFR, urine volume [ml/h], urinary output, fluid balance)	Х	X	X	Х	X	X	Х
Blood and urine samples	X	X					
AKI (severity, diagnosis by,		Χ	Х	Χ	Χ		

¹ After randomization to end of intervention (12h)

² d30, d60, d90

Date: 16.02.2017 Version: V1

CONFIDENTIA

transient/persistent, RRT dependency, RRT days)						
Scores (APACHE II, SOFA)	Х	Х	Х	Х		
Concomitant medication (vasopressors, radio contrast agents, diuretics, ACEi, ARBs)	Х	Х	Х	Х		
Renal recovery					Х	Х
Mortality						Х
Length of ICU and hospital stay						Х
Renal replacement therapy	Х	Х	Х	Х	Х	Х
MAKE						Х
Complications (myocardial infarction, cerebral ischemia, ICB, bleeding >300ml/hour, re-operation)	Х	Х	Х	Х	Х	Х

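### Section 4.6.2 and the synopsis withhold control-arm study cardiac output from the treating physician, with no exception for a value of immediate clinical concern

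*Combined protocol and SAP*

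**What the plan says.** The rule appears twice for the control arm. Section 4.6.2 (Control intervention) has cardiac output measured "via echocardiography; at initiation and then every 3h up to 12h) but the treating physician will not be informed about the values". The control-group paragraph of the synopsis reads almost identically: "by echocardiography, at initiation and then every 3h up to 12h) but the treating physician will not be informed about the values".

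On who holds the values, section 4.2.2 (Blinding) states that in the control group "the independent research staff will carry out the hemodynamic evaluation so that the trial is still blinded". Section 4.2.1 (Randomization) says of the active arm that "the intervention will be provided by research staff not involved in the care of patient". Section 4.2.2 also keeps group allocation closed until the final analysis.

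Four other provisions come closest to the point:

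- Section 4.4 on withdrawal: "A patient may also be withdrawn from the study at the request of his/her legal representative or physician, for any reason". It also provides for withdrawal by the investigator, with a final examination.
- Section 4.5.2 covers premature termination of the trial as a whole.
- Section 4.6.3 leaves usual care with the treating team: "primary physicians will determine the remainder of patient management consistent with established best practices".
- The visit table in 4.7.1.3 schedules "Hemodynamic parameters (MAP, HR, CVP, CI, CO") for recording during the intervention period and sets no alert level.

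**The concern.** Withholding routine values has a clear purpose. The legend of the validation-arm algorithm in section 4.6.1 reads "CI, cardiac index; CO, cardiac output; MAP, mean arterial pressure; PLRT, passive leg raising test", so cardiac output and cardiac index belong to the experimental strategy, and passing them on freely would blur the contrast between arms. That purpose does not require withholding a value that calls for immediate attention.

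As written, the person who sees the value and the person who can act on it are kept apart, and the rule tells the first not to inform the second. This covers the 12 hours after randomization, in patients selected for high AKI risk whom section 4.3.1 describes as mostly sedated and ventilated when they reach the ICU. What could be lost is earlier or additional information about a patient, in a situation where the trial already holds that information.

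**Working it through.** **Step 1. Is there an exception anywhere?** The plan gives no figure on this point, so the check is textual.

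| Provision | Does it release a worrying control-arm value? |
|---|---|
| 4.6.2 and synopsis | No. The rule is unqualified. |
| 4.2.2 Blinding | No. It assigns the measurement to independent staff and gives no emergency rule. |
| 4.4, withdrawal at the physician's request | No. The physician does not have the study value that might prompt it. |
| 4.4, withdrawal by the investigator | No. It is a patient-level route on the trial side, but it does not provide for passing on the value. |
| 4.5.2 Premature termination | No. It acts on the whole trial. |
| 4.6 and 4.6.3, usual care | No. The physician may order a separate measurement, but the study value is not released. |
| 4.7.1.3 Visit table | No. It covers recording only. |

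**Step 2. Reach of the rule.** Time points: 0, 3, 6, 9 and 12 h, that is 12/3 + 1 = 5. The synopsis gives 140 analysed patients per arm and 310 allocated in total.

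- Analysed controls: 5 × 140 = 700 values.
- Allocated controls: 310/2 = 155, and 5 × 155 = 775 values.

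These are all the values covered by the rule. No rate of critical values is given.

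**Step 3. What would an exception cost the AKI comparison?** Let k of 140 controls have a value disclosed. Section 2.2 reports single-center AKI rates of 71.7% (control) and 55.1% (intervention), a difference of 71.7 − 55.1 = 16.6 points.

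- (a) Ceiling, if every disclosure changed that patient's AKI outcome: k/140.
- (b) Assuming each disclosed patient gains the full single-center effect: 16.6 × k/140.

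| k | (a) points | (b) points |
|---|---|---|
| 1 | 0.7 | 0.12 |
| 7 | 5.0 | 0.83 |
| 14 | 10.0 | 1.66 |
| 24 | 17.1 | 2.85 |

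On the ceiling, k must reach 24 before the shift exceeds 16.6 points (k = 23 gives 16.4). For scale, the 95% half-width for the AKI difference at 140 per arm and the single-center rates is 1.96 × √(0.717 × 0.283/140 + 0.551 × 0.449/140) = 0.111, or 11.1 points.

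**Step 4. Link to the primary endpoint.** Section 6.2 pools both arms, n = 280, to estimate compliance. Its stated interval of 44% to 56% reproduces: Clopper-Pearson for 140/280 gives 43.99% to 56.01%. If a disclosure were scored as non-compliance in an otherwise compliant patient, each would lower the estimate by 1/280 = 0.36 points. An exception should therefore say how a disclosure is scored.

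**The case against.** The strongest reply is that no consequence is shown. Withholding is deliberate and keeps the arms distinct. Treating physicians keep their discretion, and nothing in the documents stops them from measuring cardiac output themselves. A patient outside the trial would not have had the study value either. Section 4.4 also gives the investigator a patient-level way out.

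Most of this stands as a limit on weight. Routine ICU care may well reveal the same problem, and no harm rate is known. It does not close the gap: freedom to order another measurement does not release the one already made, and withdrawal by the investigator does not provide for passing it on. If staff would in practice speak up, they would be departing from the written rule.

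A reader might go further and infer that control patients are denied standard care, that they are worse off than non-participants contrary to sections 2.4 and 5.2, or that the AKI or compliance results are biased. The documents support none of these. Usual care continues under 4.6 and 4.6.3, and nothing gives the frequency or effect of withheld values.

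A reader might also expect that one exception worded alike for both arms would keep a disclosure from revealing allocation. That does not follow. Section 4.6.2 governs controls only, and the validation arm is actively optimized under 4.6 and 4.6.1. If the optimization works, worrying values would be rarer there, so a disclosure would itself point to the control arm.

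**Conclusion.** The gap is real and minor. As written, sections 4.6.2 and the synopsis keep a control-arm study value of immediate clinical concern from the treating physician, and no other provision in the available text releases it. The rule reaches 700 values in analysed controls; how many would be of concern is unknown.

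The conclusion rests on the text as supplied. The figures in section 4.6.1 are not shown, although the caption of Figure 1 confines the algorithm to the validation arm. The cost figures rest on 140 analysed controls. Column (b) also assumes the single-center effect carries over; column (a) does not.

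The statement in section 2.4 that values are withheld in both groups differs from the control-only rule in 4.6.2. That is a separate editorial point, and this one does not depend on it.

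**What to change.** Add to the withholding sentence in section 4.6.2 and in the synopsis:

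> except that a value meeting a strict criterion for immediate clinical concern, set by the investigators before enrolment, is disclosed to the treating physician and logged; the patient stays in the ITT analysis, and the disclosure by itself does not count as non-compliance for the primary endpoint (KDIGO recommendations fulfilled).

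Report the number of disclosures with the results.

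The administrative cost is one clause in two places and one log field. The scientific cost is slight contamination of the control arm, at most 0.7 points of control AKI incidence per disclosed patient. The total depends on an unknown number of disclosures, which is why the criterion should be strict. The treating physician may also infer control allocation for that patient. Section 4.2.2 does not name the treating physician among the blinded parties, but the disclosure should go no further than the treating team, so that endpoint assessors stay blinded.

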4.6.3 Additional treatments

The patient's primary physicians will determine the remainder of patient management consistent with established best practices with the management of critically ill patients. In patients with acute lung injury (ALI) or acute respiratory distress syndrome (ARDS), tidal volume for mechanical ventilation will be approximately 6 ml per kilogram of predicted body weight and adjusted to maintain a peak plateau pressure between 25 and 30 cm of water(24). Ventilator associated pneumonia will be evaluated and treated in accordance with published clinical practice guidelines and consensus statements(25). Sepsis will be diagnosed and treated in accordance with published guidelines(26). All medications will be dose adjusted for renal failure and RRT in accordance with standard dosing guidelines.

All patients will be prescribed a nutritional intake that will provide at least 25-30 kcal/kg/day, depending on mechanical ventilation and other factors. Protein intake will be at least 1.2 g/kg/day. In patients receiving parenteral nutrition, carbohydrate infusion rates will not exceed 5 mg/kg/min. Water-soluble vitamins will be supplemented to replace dialysis-related losses.

4.7 Efficacy and safety variables

4.7.1 Measurement of efficacy and safety variables

- 4.7.1.1 Primary target variable
 - Compliance rate (proportion of patients who are treated according to the trial protocol):
 KDIGO recommendations fulfilled at all time
- 4.7.1.2 Secondaryand other target variables
- Occurrence of AKI within the first 72 hours after cardiac surgery (AKI will be defined according to the KDIGO guidelines)
- Moderate and severe AKI within 72 hrs (according to the KDIGO guidelines)
- Severity of AKI within 72 hrs
- Renal recovery

Renal recovery at hospital discharge and at days 30, 60 and 90 will be defined asserum creatinine levels < 0.5 mg/dl higher than baseline.

- 30-day, 60.day and 90-day mortality
- Length of stay in intensive care unit and hospital

CONFIDENTIAL

Date: 16.02.2017 Version: V1

Information on ICU and hospital stays will be documented. From admission to ICU admission until follow-up (by phone) at day 90, the location of the patient within the hospital will be documented in the CRF. The following will be recorded for each patient

- Date and time of admission to ICU
- Date and time of discharge from ICU
- Date and time of discharge from hospital
- Need and duration of RRT during hospital stay
- RRT at days 30, 60 and 90
- MAKE₃₀, MAKE₆₀ and MAKE₉₀ (major adverse kidney events consisting of mortality, dialysis dependency persistent renal dysfunction (defined as serum creatinine ≥ 2x compared to baseline value)
- Determination of different biomarkers

Blood and urine samples for biomarkers will be collected at the time of randomization and 12 hrs later

 Assessment of complications related to the implementation of the KDIGO guidelines will be documented.

